6.3 STARTING DOSES AND SCHEDULE

6.3.1.1 Experimental Arm (PM01183): Arm A

- 3.2 mg/m^2 on Day 1 q3wk (three weeks = one treatment cycle)

Dose will be rounded to the first decimal.

6.3.1.2 *Control Arm (PLD and topotecan): Arm B*

- **PLD starting dose and schedule:**

50 mg/m² on Day 1 q4wk (four weeks = one treatment cycle).

Dose will be rounded to the first decimal.

Patients previously treated with PLD will be assigned to receive topotecan if they are randomized to the control arm.

- **Topotecan starting dose and schedule:**

- 1.50 mg/m² daily on Days 1-5 q3wk (three weeks = one treatment cycle) for patients with calculated CrCL \geq 60 ml/min.
- 1.25 mg/m² daily on Days 1-5 q3wk for patients with calculated CrCL between 40 and 59 ml/min.
- 0.75 mg/m² daily on Days 1-5 q3wk for patients with calculated CrCL between 30 and 39 ml/min.

Dose will be rounded to the first decimal.

Skipped doses of topotecan will not be replaced.

Patients previously treated with topotecan will be assigned to receive PLD if they are randomized to the control arm.

However, if the number of patients randomized to either PLD or topotecan reaches 60% of the total number of patients expected in the control arm (i.e. 126 patients), then the treatment of choice in the control arm will be restricted to the less frequent control drug until the end of accrual (see Section [5.6](#)).

The dose for all three agents (PM01183, PLD or topotecan) will be capped at a body surface area (BSA) of 2.0 m² in those patients who have a greater BSA. BSA will be calculated according to the standard nomogram used at each center.

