6.5 CRITERIA FOR TREATMENT CONTINUATION

Further treatment cycles (i.e., Cycle 2 or subsequent) will be administered every three weeks (PM01183 or topotecan) or every four weeks (PLD) (with a window of \pm 48

hours in all three treatment arms) if the patient fulfills all the re-treatment criteria defined in [Table 8](#) (PM01183), [Table 9](#) (PLD) or [Table 10](#) (topotecan).

Table 8. Criteria for treatment continuation with PM01183 (Arm A).

Variable	Day 1
ECOG PS	≤ 2
ANC	≥ 1.5 x 10 ⁹ /l
Platelets	≥ 100 x 10 ⁹ /l
Hemoglobin ^a	≥ 8 g/dl
Total bilirubin	≤ 1.5 x ULN or direct bilirubin ≤ ULN if total bilirubin > ULN
Albumin	≥ 2.7 g/dl
AST/ALT	≤ 3.0 x ULN
CPK	≤ 2.5 x ULN
Calculated CrCl (Cockcroft and Gault's formula)	≥ 30 ml/min
Other non-hematological drug-related AEs (except isolated increased GGT and/or AP; grade 2 alopecia, constipation, fatigue, neuropathy, and not optimally treated nausea)	Grade ≤ 1

^a Patients may receive PRBC transfusion and/or EPO treatment if clinically indicated to increase/maintain adequate hemoglobin levels.

AEs, adverse events; ANC, absolute neutrophil count; AP, alkaline phosphatase; AST/ALT, aspartate aminotransferase/alanine aminotransferase; CPK, creatine phosphokinase; CrCL, creatinine clearance; ECOG PS, Eastern Cooperative Oncology Group performance status; EPO, erythropoietin; PRBC, packed red blood cells; ULN, upper limit of normal.

Table 9. Criteria for treatment continuation with PLD (Arm B).

Variable	Day 1
ECOG PS	≤ 2
ANC	≥ 1.5 x 10 ⁹ /l
Platelets	≥ 75 x 10 ⁹ /l
Hemoglobin^a	≥ 8 g/dl
Total bilirubin	≤ 1.5 x ULN or direct bilirubin ≤ ULN if total bilirubin > ULN
Mucositis or hand-foot syndrome	Grade < 2
Calculated CrCl (Cockcroft and Gault's formula)	≥ 30 ml/min
Other non-hematological drug-related AEs (except isolated increased GGT and/or AP; grade 2 alopecia, constipation, fatigue, neuropathy, and not optimally treated nausea)	Grade ≤ 1

Variable	Day 1
----------	-------

^a Patients may receive PRBC transfusion and/or EPO treatment if clinically indicated to increase/maintain adequate hemoglobin levels.

AEs, adverse event(s); ANC, absolute neutrophil count; AP, alkaline phosphatase; CrCl, creatinine clearance; ECOG PS, Eastern Cooperative Oncology Group performance status; EPO, erythropoietin; GGT, gamma-glutamyltransferase; PPE, palmar-plantar erythrodysesthesia; PRBC, packed red blood cells; ULN, upper limit of normal.

Table 10. Criteria for treatment continuation with topotecan (Arm B).

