6.6 DOSE REDUCTION

Patients who experience any grade ≥ 3 treatment-related non-hematological toxicity (according to the NCI-CTCAE v. 4) and/or grade 3 thrombocytopenia associated with bleeding or persistent at the time of re-treatment or grade 4, or frequent or prolonged treatment-related dose delays (> 1 week) (or skipped infusions if on topotecan) will continue treatment after appropriate dose reduction (see [Table 11](#) for dose reduction in Arm A, PM01183; see [Table 12](#) for dose reduction in Arm B, PLD or topotecan).

Patients experiencing grade 4 neutropenia or any grade febrile neutropenia, or neutropenic infection during the preceding cycle or frequent treatment-related dose delays exclusively due to neutropenia may continue treatment without any dose reduction, but the patient must receive secondary prophylaxis with CSF starting at least 24 hours after the last infusion of the cycle. If despite appropriate CSF secondary prophylaxis, grade 4 neutropenia or febrile neutropenia, neutropenic infection or the dose delay re-occurs, then dose reduction should be implemented.

Exceptions for dose reduction are: grade 3 nausea and/or vomiting not optimally prevented, grade 3 fatigue lasting \leq 2 days, grade 3 diarrhea lasting \leq 1 day or not optimally treated, isolated grade 3 ALT or AST elevations not leading to dose delays and/or non-clinically relevant isolated biochemical abnormalities (e.g., GGT).

Table 11. Levels of dose reduction in Arm A (PM01183).

	Arm A PM01183 dose (q3wk) (mg/m ²) ^a
1 (starting dose)	3.2
-1	2.6
-2	2.0

^a PM01183 dose will be capped at a body surface area (BSA) of 2.0 m² in those patients who have a greater BSA.

q3wk, every three weeks.

Table 12. Levels of dose reduction in Arm B (PLD or topotecan).

	Arm B			
	PLD^e (q4wk) (mg/m ²)	Topotecan^e daily dose (q3wk) (mg/m ²)		
1 (starting dose)	50	1.50 ^a	1.25 ^b	0.75 ^{c, d}
-1	37.5	1.25	1.00	-
-2	28 ^d	1.00	0.75 ^d	-

^a Starting dose for patients treated with topotecan with calculated CrCL \geq 60 ml/min.

^b Starting dose for patients treated with topotecan with calculated CrCL of 40-59 ml/min.

^c Starting dose for patients treated with topotecan with calculated CrCL of 30-39 ml/min.

^d No dose reduction below 28 mg/m² of PLD or 0.75 mg/m²/day of topotecan will be implemented under any circumstances.

^e PLD and topotecan dose will be capped at a body surface area (BSA) of 2.0 m² in those patients who have a greater BSA.

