CrCL, creatinine clearance; PLD, pegylated liposomal doxorubicin; q3wk, every three weeks; q4wk, every four weeks.

In case of grade \geq 2 hand-foot syndrome (HFS) or stomatitis secondary to PLD treatment, the PLD treatment administration will be delayed until resolved to grade \leq 1 or discontinued if not resolved within two weeks. In addition, subsequent doses will be reduced if the HFS or stomatitis is \geq grade 3 ([Table 13](#)).

Table 13. PLD dose modification guidelines according to hand-foot syndrome and stomatitis (Arm B).

Toxicity grade	Hand-foot syndrome (HFS)	Stomatitis	Dose adjustment
1	Mild erythema, swelling, or desquamation not interfering with daily activities.	Painless ulcers, erythema, or mild soreness.	Re-treat unless patient has experienced previous grade 3 or 4 HFS/mucositis. If so, delay up to two weeks and decrease dose one level. Return to original dose interval.
2	Erythema, desquamation, or swelling interfering with, but not precluding normal physical activities; small blisters or ulcerations less than 2 cm in diameter.	Painful erythema, edema, or ulcers, but can eat.	Delay dosing up to two weeks or until resolved to grade 0-1. If after two weeks there is no resolution, PLD should be discontinued. If resolved to grade 0-1 within two weeks, and there are no prior grade 3-4 HFS/mucositis, continue treatment at previous dose and return to original dose interval. If patient experienced previous grade 3-4 toxicity, continue treatment with one dose level reduction and return to original dose interval.
3	Blistering, ulceration, or swelling interfering with walking or normal daily activities; cannot wear regular clothing.	Painful erythema, edema, or ulcers, and cannot eat.	Delay dosing up to two weeks or until resolved to grade 0-1. Decrease dose one level and return to original dose interval. If after two weeks there is no resolution, PLD should be discontinued.
4	Diffuse or local process causing infectious complications, or a bed ridden state or hospitalization.	Requires parenteral or enteral support.	Delay dosing up to 2 weeks or until resolved to grade 0-1. Decrease dose one level and return to original dose interval. If after two weeks there is no resolution, PLD should be discontinued.

HFS, hand-foot syndrome; PLD, pegylated liposomal doxorubicin.

Patients treated with PLD who have LVEF decreased to < 45% or with a 20% decrease from the baseline value have to permanently discontinue PLD treatment.

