Control and experimental arms:

Patients who experience any treatment-related grade 3 or 4 hypersensitivity and/or extravasations will permanently discontinue irrespectively of arm allocation.

Up to two dose reductions are allowed per patient. Patients who continue to experience treatment-related toxicity and/or frequent dose delays after two dose reductions must be withdrawn from the study. Once the dose has been reduced for an individual patient, it will not be re-escalated under any circumstances irrespectively of arm allocation.

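### The PLD rules for hand-foot syndrome and stomatitis conflict in three situations, and the protocol does not say which passage governs

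*Protocol*

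**What the plan says.** The relevant rules stand in four places in the protocol body.

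- **Section 6.5, Table 9 (PLD re-treatment).** The row labelled "Mucositis or hand-foot syndrome" requires a grade below 2 on Day 1. It sets no condition on earlier episodes.
- **Section 6.5, closing paragraph.** Treatment stops if there is no recovery after a two-week delay. The exception is a patient with documented objective clinical benefit, if the sponsor agrees; treatment may then go on at a reduced dose.
- **Section 6.6, running text.** The opening paragraph says that patients with "frequent or prolonged treatment-related dose delays (> 1 week) (or skipped infusions if on topotecan) will continue treatment after appropriate dose reduction". The text above Table 13 delays PLD from grade 2 upwards and stops it if there is no resolution in two weeks. It then says "In addition, subsequent doses will be reduced if the HFS or stomatitis is" grade 3 or worse, and points to Table 13. The closing text says "Up to two dose reductions are allowed per patient" and bars re-escalation.
- **Section 6.6, Table 13.** Grade 1 row: "Re-treat unless patient has experienced previous grade 3 or 4 HFS/mucositis. If so, delay up to two weeks and decrease dose one level". Grade 2 row, resolved within two weeks and no earlier grade 3-4: "continue treatment at previous dose and return to original dose interval". Grade 3 and 4 rows: hold for up to two weeks or until grade 0-1, go down one level, and stop if unresolved at two weeks.

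The starting dose in section 6.3.1.2 is "50 mg/m² on Day 1 q4wk (four weeks = one treatment cycle". Table 12 gives the lower levels as 37.5 and 28 mg/m², and its footnote says "No dose reduction below 28 mg/m² of PLD or 0.75 mg/m²/day of topotecan will be implemented under any circumstances". Section 5.2.1.2 ends treatment when more than two reductions are needed. The synopsis carries the same rules in Tables 3 and 7 and the text around them.

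**The concern.** A site that follows one of these passages can breach another, and nothing states an order of precedence. Section 5.2.2 names incorrect dosing through not following the dose-adjustment specifications as a deviation that might affect patient well-being or safety. Here the specifications themselves disagree.

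What is at stake is consistent dosing and toxicity management for patients on PLD, one of the two comparator drugs in an open-label trial. SAP section 8.3 and the tables in its Appendix I report delays, reductions and relative dose intensity for PLD. Differences between sites in how the rules are read would therefore enter the reported exposure results.

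**Working it through.** **Inputs and the plan's own figures.** Dose levels 50 / 37.5 / 28 mg/m² (Table 12): 50 × 0.75 = 37.5, and 37.5 × 0.75 = 28.125, stated as 28. As a share of the start: 37.5/50 = 75% and 28/50 = 56%. Planned intensity over a four-week cycle: 50/4 = 12.5, 37.5/4 = 9.375 and 28/4 = 7.0 mg/m²/week. Cap on either control drug (section 5.6): 60% × 420/2 = 126 of 210.

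**Conflict 1: grade 1 on Day 1 after an earlier grade 3-4 episode.** Table 9 accepts the patient, and the 6.6 text neither delays nor reduces at grade 1. The Table 13 grade 1 row does both. It names no recovery target for the delay and does not say whether the reduction already made for the grade 3-4 episode satisfies it. Take one grade 3 episode at 50 mg/m² that resolves within two weeks, and apply the grade 1 row only at cycles after the first reduced dose:

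| Later course | Table 9 plus 6.6 text | Table 13 read literally |
|---|---|---|
| No grade 1 at any later Day 1 | 37.5, 37.5, 37.5 | 37.5, 37.5, 37.5 |
| Grade 1 at the second Day 1 after the episode only | 37.5, 37.5, 37.5 | 37.5, 28, 28 |
| Grade 1 at every later Day 1 | 37.5, 37.5, 37.5 | 37.5, 28, stop |

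The stop in the last row arises because a third reduction would be called for, while only two are allowed and 28 mg/m² is the floor. The grade 2 row also adds a reduction after earlier grade 3-4, which the 6.6 text does not mention.

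**Conflict 2: first grade 2 episode resolving after 8 to 14 days.** The delay exceeds 7 days, so the opening paragraph of 6.6 calls for a reduction. It is within 14 days with no earlier grade 3-4, so Table 13 keeps the dose. Section 6.6 lists its exceptions to dose reduction: certain grade 3 nausea or vomiting, fatigue, diarrhea, isolated ALT/AST elevations and minor biochemical abnormalities. Hand-foot syndrome and stomatitis are not among them.

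**Conflict 3: no resolution at two weeks.** The 6.6 text and Table 13 agree that PLD ends. Section 6.5 allows continuation at a reduced dose when benefit is documented and the sponsor agrees. Neither section refers to the other on this point.

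**What cannot be computed.** The documents give no rate of hand-foot syndrome or stomatitis under PLD, and none for residual grade 1 or for grade 2 delays over a week.

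**The case against.** Part of conflict 1 is undefined precedence rather than flat contradiction. Table 9 is one necessary condition among several and sets no dose, and the 6.6 text cites Table 13 as its detail. A reader could also say that a specific table overrides a general paragraph, which would settle conflict 2. These arguments have some force. But Table 9 does help decide whether a cycle is given on Day 1, and there the grade 1 row orders a delay that Table 9 and the text do not. No passage says that the specific rule prevails.

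Four stronger readings are tempting, and the documents do not support them.

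- *A grade 3 episode on its own leads to three different outcomes.* It does not. If it clears to grade 0 and no later toxicity follows, every reading gives 37.5 mg/m².
- *The dose falls to 28 mg/m² at the recovery visit itself.* The grade 3 row already covers recovery to grade 0-1 and orders one decrease. Adding the grade 1 row at that visit would also add a second delay to one already served. That is a strained reading.
- *All later reductions punish one episode.* Grade 1 at a later cycle appears after a further dose and may be new toxicity. Withdrawal for continuing toxicity after two reductions applies to both arms.
- *The conflict favours PM01183 on PFS.* Stopping PLD does not censor PFS, because scans continue every eight weeks (section 7.1). Starting new therapy before progression does (section 3.1), but the direction and size of any effect are not shown. Time also limits the full sequence. If the grade 3 episode falls in cycle 1, the stop comes at the fourth Day 1, at least 12 weeks after the start (84/30.4 = 2.8 months, before delays), against an assumed control median PFS of about 3.5 months.

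**Conclusion.** The point holds as a conflict of wording in three defined situations, repeated in the synopsis. Conflict 2 is the plainest. Conflict 1 has the widest spread: 37.5 mg/m² throughout (75% of the starting dose), against 37.5, then 28 mg/m² (56%), then the end of PLD. That spread depends on residual or recurrent grade 1 at later cycles and on a literal reading of Table 13.

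The direct consequence is inconsistent PLD dosing and toxicity management across sites. Under the cap, PLD may be given to up to 126 of 210 control patients, but only those in one of the three situations are affected. Their number, and any effect on PFS, cannot be derived from the documents. No alpha, power or event count changes.

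**What to change.** Reconcile Table 9 and synopsis Table 3, Table 13 and synopsis Table 7, the section 6.5 exception and the section 6.6 text, together with the synopsis text that repeats them, so that they agree. The revised wording should state:

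1. which passage governs Day 1 re-treatment at grade 1 after an earlier grade 3-4 episode, and whether a reduction is counted once per episode;
2. whether Table 13 or the rule on delays over one week governs a first grade 2 episode that resolves after 8 to 14 days;
3. whether the section 6.5 exception applies to PLD patients whose hand-foot syndrome or stomatitis has not resolved at two weeks.

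The choice of rule is the sponsor's, and none is proposed here. The cost is protocol wording, by amendment or clarification letter to sites, with no added visits or patients.

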
Patients treated with PLD who have LVEF decreased to < 45% or with a 20% decrease from the baseline value have to permanently discontinue PLD treatment.
 
Control and experimental arms:
 
Patients who experience any treatment-related grade 3 or 4 hypersensitivity and/or extravasations will permanently discontinue treatment irrespectively of arm allocation.
 
Up to two dose reductions are allowed per patient. Patients who continue to experience treatment-related toxicity and/or frequent dose delays after two dose reductions must be withdrawn from the study. Once the dose has been reduced for an individual patient, it will not be re-escalated under any circumstances irrespectively of arm allocation.
				
ALLOWED MEDICATIONS/ THERAPIES	
 Therapies for pre-existing and treatment-emergent medical conditions, including pain management. Blood products and transfusions, as clinically indicated. Bisphosphonates. In case of nausea or vomiting, extended symptomatic treatment for emesis will be allowed. Colony-stimulating factors (CSFs) or erythropoietin treatment according to the American Society of Clinical Oncology (ASCO) guidelines. Anticoagulants. 			

PROHIBITED MEDICATIONS/ THERAPIES	
 Concomitant administration of any antineoplastic therapy (other than those specifically allowed). Any radiotherapy other than limited field irradiation for cancer pain control exclusively. Immunosuppressive therapies other than corticosteroids for antiemetic prophylaxis and/or pain control. Aprepitant and equivalent agents (e.g., fosaprepitant) for patients allocated to the PM01183 arm (Arm A). Primary CSF prophylaxis for patients allocated to the PM01183 arm (Arm A), unless recommended by the IDMC after the interim safety analysis. Any other investigational agent/s.

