5.2 PLANNED TRIAL PERIODS (INDIVIDUALLY PER PATIENT)

[figure not shown]
Patients will be evaluated at scheduled visits during three study periods:

- **Pre-treatment:** from signature of IC to the first infusion of the study treatment.
- **Treatment:** from the first infusion of the study treatment to the *end of treatment* (EOT) (see Section [5.2.1.1](#)).
- **Follow-up:** after EOT, patients will be followed every four weeks until resolution or stabilization of all toxicities, if any. Patients who finish treatment without radiological disease progression will be followed every eight weeks from randomization until disease progression or start of a new antitumor therapy, death or until the date of study termination (clinical cutoff), whichever occurs first. After radiological disease progression is documented or a new antitumor therapy is started, patients will be followed at least every three months (\pm two weeks) until death or date of study termination, whichever occurs first. Once the whole

recruitment is completed, the 3-month follow-up for patients who discontinue treatment due to disease progression will be performed according to a calendar time.

Patients will be considered to be **on-study** from the signature of the informed consent form (ICF) until death or study termination. Patients will be considered to be **on-treatment** from Day 1 of Cycle 1 until the day of EOT. This EOT is defined as 30 days after the day of the last study treatment infusion (see [Figure 5](#)), unless the patient starts a new antitumor therapy or dies (whichever occurs first). An end-of-treatment visit (EOT visit) will be performed within 30 days (\pm 7 days) after the last study treatment administration, unless the patient starts any subsequent antitumor therapy, in which case the end-of-treatment visit should be performed immediately before the start of the new therapy.

Figure 5. Study periods.

FUP, follow-up; ICF, informed consent form; PRE TT, pre-treatment; TT, treatment; wks, weeks.

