5.2.1 Discontinuations

5.2.1.1 Treatment Discontinuation

Treatment discontinuation occurs when an enrolled patient ceases to receive the study treatment (PM01183, PLD or topotecan) regardless of the circumstances. By convention, the date of end of treatment is defined as 30 days after the day of the day of last dose of the study treatment (treatment discontinuation), start of a new antitumor therapy or death, whichever occurs first, in which case the date of administration of this new therapy or the date of death will be considered the date of EOT.

The primary reason for any treatment discontinuation will be recorded on the patient's Case Report Form (CRF).

Should a patient decide to prematurely discontinue the study treatment (refuses treatment), all efforts will be made to complete and report the observations as thoroughly as possible. She should be asked if she can still be contacted for further information. The outcome of that discussion should be documented in the medical records.

5.2.1.2 *Reasons for Treatment Discontinuation*

Patients will receive the study treatment(s) while it is considered to be in their best interest. Specifically, treatment will continue until:

- Disease progression.
- Unacceptable toxicity.
- Intercurrent illness of sufficient magnitude to preclude safe continuation of the study.
- Investigator's decision.
- Patient refusal.
- Non-compliance with study requirements.
- A major protocol deviation that may affect the risk/benefit ratio for the participating patient.
- Requirement of > two dose reductions.

Patients who are withdrawn for any reasons must not be re-treated in the context of this study at any time. For follow-up activities, please refer to Section [5.9](#).

5.2.1.3 *Study Discontinuation*

Study discontinuation occurs when an enrolled patient ceases to participate in the study, regardless of the reason (as detailed under "Follow-up" in Section [5.2](#)). The date and reason for study discontinuation will be clearly documented in the medical records of the patient.

5.2.2 *Protocol Deviations*

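### Section 6.6 and the synopsis order withdrawal from the study for toxicity or delays after two dose reductions; this contradicts Sections 5.2, 5.2.1.2 and 5.9 and could lead a site to stop PFS and OS follow-up

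*Protocol*

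**What the plan says.** Section 6.6, in the paragraph covering both arms, allows up to two dose reductions per patient and then states: "Patients who continue to experience treatment-related toxicity and/or frequent dose delays after two dose reductions must be withdrawn from the study". The dose-reduction row of the synopsis has the same instruction: "frequent dose delays after two dose reductions must be withdrawn from the study".

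The protocol keeps two events apart. Section 5.2.1.1 defines treatment discontinuation as no longer receiving study drug. Section 5.2.1.3 defines leaving the study: "Study discontinuation occurs when an enrolled patient ceases to participate in the study, regardless of the reason". The list of reasons for **treatment** discontinuation in Section 5.2.1.2 includes "Requirement of > two dose reductions". The same reason ends treatment in Section 3, in the synopsis row on duration of study period, and in SAP Section 2.

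For patients who stop treatment without radiological progression, Section 5.9 requires 8-weekly tumour assessments until progression, new antitumour therapy, death or clinical cutoff. After progression or new therapy it requires survival contact at least every three months. Section 5.2 says the same.

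**The concern.** Patients who have used both reductions and still have toxicity or delays fall under two instructions. One ends treatment and leaves follow-up running. The other, worded as an obligation, takes them out of the study. Nearby rules name treatment as the thing that stops: the LVEF rule in Section 6.6 does so, and so does the hypersensitivity rule in the synopsis. The two-reduction sentence alone names the study, so a site has some reason to think the difference is deliberate.

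PFS by IRC is the primary endpoint, analysed by intention to treat, and OS is secondary. A patient lost before progression is censored for PFS at the last tumour assessment, and for OS at last contact. Here the loss would be triggered by toxicity, which is unlikely to be independent of prognosis and may differ by arm. Such censoring can bias the treatment comparison in either direction, and keeping the patient in the ITT population does not repair it.

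**Working it through.** **1. The passages side by side**

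| Place | What happens after two reductions, or after treatment stops |
|---|---|
| Protocol 6.6; synopsis, dose reduction | Withdrawal from the study |
| Protocol 5.2.1.2; Protocol 3; synopsis, duration of study period; SAP 2 | Treatment stops |
| Protocol 5.2 and 5.9 | Tumour and survival follow-up continue |
| SAP Tables 10.2.1 and 10.2.4 | Treatment discontinuation and off-study reasons are tabulated separately; neither toxicity nor dose reduction is a named off-study reason, but there is an Other row |
| SAP Listings 13.1.42 and 13.1.48 | Separate End of Treatment and Off Study forms |

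The first row cannot be reconciled with the next two. The last two rows show how the wording could reach the data: it bears on whether a site also completes the Off Study form.

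**2. Would the analysis plan reveal or absorb the loss?** The three PFS sensitivity analyses in SAP Section 6.2 change the progression date (scheduled date, earlier of IRC and investigator, prior assessment). None examines dropout related to toxicity. The censoring reasons in SAP Table 11.3.1.44 have no row for leaving the study, so such patients would probably be counted as progression-free at last assessment or under Other.

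**3. The plan's event count.** Inputs from Section 8.1: HR 0.70, one-sided 2.5%, 90% power, 1:1 allocation.

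d = 4(1.960 + 1.282)² / (ln 0.70)² = 4 × 10.51 / 0.1272 ≈ 331, against the stated 332. The figure reproduces. Power at d events is Φ(½√d × 0.3567 − 1.960), which gives 90.1% at 332.

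**4. Power if events were lost and not made up.** The loss fractions are assumptions; the documents give none.

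| Events lost | Events left | Power |
|---|---|---|
| 1% | 329 | 89.9% |
| 2% | 325 | 89.6% |
| 5% | 315 | 88.6% |
| 10% | 299 | 86.9% |
| 15% | 282 | 85.0% |

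The analysis is tied to an event count, so lost events could instead be made up by waiting. With uniform accrual over 18 months, exponential PFS, control median 3.5 months (λ = ln 2/3.5 = 0.198 per month, times 0.70 in Arm A) and no dropout, expected events per arm at month T are 210 × [1 − (e^(−λ(T−18)) − e^(−λT)) / (18λ)]. At month 24 this gives 192.6 + 176.4 = 369 events. A 10% loss would leave 369 × 0.90 = 332.

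**5. How early could the instruction apply?** Two reductions followed by further toxicity take about three cycles: 9 weeks (2.07 months) on a 3-week schedule, 12 weeks (2.76 months) on PLD. The expected share with a PFS event by then is 1 − 2^(−t/3.5) in the control arm, that is 34% at 9 weeks and 42% at 12 weeks. In Arm A at HR 0.70 it is 1 − 2^(−0.70 × 2.07/3.5) = 25% at 9 weeks. Patients who have already progressed cannot lose their PFS event, but could still lose OS follow-up.

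**The case against.** A reader might infer that the protocol's own definition of study discontinuation ends participation for these patients and so removes them from PFS and OS follow-up. The documents do not support that, for four reasons.

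- Directly below the list of treatment-discontinuation reasons, Section 5.2.1.2 says: "Patients who are withdrawn for any reasons must not be re-treated in the context of this study at any time". It then adds "For follow-up activities, please refer to Section" 5.9. Withdrawal there means off treatment and into follow-up.
- The definition in Section 5.2.1.3 goes on to refer back to the follow-up description in Section 5.2. It mentions neither toxicity nor dose reductions. Section 5.2 counts patients as on-study "from the signature of the informed consent form (ICF) until death or study termination".
- Footnote 11 to the schedule of assessments uses the same withdrawal phrase for patients who are still followed every four weeks for adverse events.
- The SAP's ITT population keeps every randomized patient.

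All of this stands, and it shows what was probably intended. It does not remove the contradiction. The sentence in Section 6.6 is mandatory and appears twice, and a site must find several other sections to overrule it. Footnote 11 covers adverse-event recovery only, not scans or survival.

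It is also fair to object that nothing shows how many patients would be affected, or that the arms would differ. The phase II study reported more grade 3/4 neutropenia on PM01183 (84.6% against 41.4%) and more febrile neutropenia (21.2% against 10.3%). Those figures come from a 7.0 mg flat dose and are not rates of exit after two reductions. They show only that toxicity can differ by arm.

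**Conclusion.** Wrong as written: an internal contradiction, of minor severity. The two-reduction sentence conflicts with the sections that class the same situation as the end of treatment and keep follow-up going. The sections read together favour continued follow-up, so harm arises only if a site acts on the sentence literally.

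The size is unknown. The number of patients reaching this point and the share of sites misreading the instruction are both absent from the documents. No design figure changes, and under the assumed losses above the effect on power is modest and recoverable by waiting for events. What remains is a risk of toxicity-related, possibly arm-dependent censoring of PFS and OS that no planned sensitivity analysis would examine.

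**What to change.** Reconcile the sentence in Section 6.6 and in the dose-reduction row of the synopsis with Sections 5.2, 5.2.1.2 and 5.9. It should refer to discontinuation of study treatment and state that 8-weekly tumour assessments and survival follow-up continue under Section 5.9.

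The cost is one sentence in two places, as a protocol clarification. No change to the dosing or stopping criteria is proposed, and the sample size and analyses are unaffected.
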